## APPENDIX K PRK SURGICAL PROCEDURE

The following steps represent a typical PRK surgical procedure and should be used as a standard model. Both eyes will be treated on the same day provided that treatment of the first eye is without an adverse event or clinically significant surgical complication.

- 1. Standard preoperative preparation and intraoperative medications will be used.
- 2. Activate the recording device (e.g., DVD recorder) and begin video acquisition of the subjects procedure.
- 3. After anesthesia and placement the lid speculum, an Amoils Epithelial Scrubber (Innova, Inc., Toronto, Ontario, Canada) with a 9.0 mm brush will be used to remove the corneal epithelium prior to laser treatment.
- 4. Ensure magnification on the operating microscope is 1.6X. Ensure the subject's pupil is centered in the reticle as the subject is fixating on the fixation LED. Focus on the anterior stromal surface.
- 5. Remind patient to fixate on flashing LED, activate ActiveTrak and Iris Registration on the STAR S4 IR Excimer Laser System.
- 6. Confirm proper placement of the outer iris boundary (OIB).
- 7. After ensuring that the reticle is centered over the subject's pupil and the subject is viewing the fixation light, fully depress the foot pedal to perform the laser treatment. If necessary, stop the laser and dry the cornea if there is fluid accumulation.
- 8. Apply mitomycin C 0.01% for 15 seconds immediately after the ablation.
- 9. Rinse the stromal surface with 30 cc of balanced salt solution.
- 10. Instill ophthalmic antibiotic QID for 1 week, fluorometholone 0.1% for 8 weeks (QID initially and tapering 1 drop every 2 weeks starting at week 3) and analgesic as needed. Continued use beyond these guidelines is allowed if medically necessary.
- 11. A bandage contact lens will be placed on the operated eye.
- 12. Note the treatment time, whether the eye tracker lost track of the eye at any time during the procedure. Record environmental conditions (temperature and humidity.)
- 13. Print the STAR S4 IR Operative Report.
- 14. Note any adverse events or complications that occurred during treatment. Report any adverse events to the Sponsor.
- 15. Patients will receive antiemetics, pain medication, and lubrication at the discretion of the investigator.

17NOV2015/ 3.0 PR/STAR-115-MIPS

# APPENDIX L ADVERSE EVENT AND COMPLAINT REPORTING INSTRUCTIONS

All adverse events and complaints related to using AMO products must be reported to AMO.

## ALL ADVERSE EVENTS AND COMPLAINTS:

For events that are not considered serious or related to the study device:

- 1. Record the event and/or complaint on the case report form that corresponds to the visit during which awareness of the event occurred. Additionally, a complaint may be reported via a telephone call to AMO.
- 2. Ensure the data are submitted to AMO electronically within a timely manner.

# SERIOUS ADVERSE EVENTS OR DEVICE DEFICIENCIES THAT MAY HAVE LED TO A SERIOUS EVENT

In the event of a serious event (i.e., life- or sight-threatening incident) whether or not related to the device, or a device deficiency that may have led to a serious event, the investigator shall:

- 1. Notify AMO immediately (no more than 48 hours after learning of the event) as follows:
  - a. Contact the following AMO personnel by phone:

b. Complete a Detailed Adverse Event Form and submit electronically to AMO

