## 4. SERIOUS, DEVICE-RELATED ADVERSE EVENTS

Success criteria: <1% of eyes with serious, device-related adverse events

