#### Serious Adverse Event (SAE)

An adverse event is considered serious (following ISO 14155) if it is an untoward occurrence which may or may not be related to use of the study device that

- is sight- or life-threatening,
- results in death,
- requires inpatient hospitalization or prolongation of hospitalization (a planned hospitalization for a pre-existing condition is not considered a serious adverse event),
- results in permanent impairment of a body structure or body function,
- necessitates medical or surgical intervention to prevent permanent impairment to a body structure or function, or
- results in fetal distress, fetal death or a congenital abnormality or birth defect

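### Appendix L equates a serious event with a life- or sight-threatening one, so a site following it literally could miss the 48-hour notice, or code as non-serious, an event that is serious on another Section 11.1 criterion

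*Protocol*

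**What the plan says.** Protocol Section 11.1 lists six alternative grounds for calling an adverse event serious, whether or not it is related to the device:

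1. It "is sight- or life-threatening".
2. It "results in death".
3. It "requires inpatient hospitalization or prolongation of hospitalization".
4. It "results in permanent impairment of a body structure or body function".
5. It "necessitates medical or surgical intervention to prevent permanent impairment to a body structure or function, or".
6. It leads to a fetal or congenital outcome.

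Section 11.3 requires the sponsor to be told of any serious adverse event within 48 hours, by telephone and with a Detailed Adverse Event Form. For the notification steps it refers sites to Appendix L.

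Appendix L has three paths:

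- **Serious events, and device deficiencies that might have led to one.** The path begins "In the event of a serious event (i.e., life- or sight-threatening incident) whether or not related to the device" and requires a call within 48 hours plus the Detailed Adverse Event Form.
- **Device-related events not considered serious.** The Detailed Adverse Event Form is completed and submitted in a timely way, with no 48-hour call.
- **Events considered neither serious nor device-related.** The instruction is: "Record the event and/or complaint on the case report form that corresponds to the visit".

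The fourth primary safety endpoint in Protocol Section 6.1 has the success criterion "<1% of eyes with serious, device-related adverse events". Protocol Section 20.2 and SAP Section 5.2 apply it cumulatively. An eye counts only if its event is both serious and device-related.

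**The concern.** The abbreviation i.e. defines; it does not illustrate. Read as written, Appendix L makes an event serious only if it threatens life or sight. It does not refer back to Section 11.1, and it is the page a site coordinator is likely to have open when an event occurs.

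Two things are at stake. The first is speed and reach of reporting: an event that is serious only because of, say, permanent impairment or a preventive intervention could lose its 48-hour notice. The second is classification. Seriousness is half of the definition of a primary safety endpoint whose limit is a handful of eyes, and SAP Section 5.2 does not say which definition of serious governs the count.

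**Working it through.** The plan states no figure to reproduce on this point. The check is a comparison of text, followed by a small count for scale.

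**Step 1. Compare the definitions.** Section 11.1 gives six alternative criteria and Appendix L names the first. Death is arguably implied by life-threatening. Hospitalization, permanent impairment, intervention to prevent impairment, and fetal outcomes are not. Section 11.3 applies the 48-hour rule to every serious adverse event without narrowing. Appendix L therefore conflicts with both sections.

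**Step 2. Trace an event that meets one of the omitted criteria, at a site that applies Appendix L literally.**

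| Site's causality judgement | Appendix L path | 48-hour call | Detailed Adverse Event Form | Medical monitor (Protocol 15.3) | SAP 6.13 listing | Could count in the endpoint if coded correctly |
|---|---|---|---|---|---|---|
| Not device-related | Visit form only | Lost | No | May not reach the monitor, whose stated remit is reports of serious or device-related events | Not if coded non-serious | No |
| Device-related | Non-serious, device-related | Lost | Yes | Yes | Yes | Yes, but coded non-serious it is not counted |

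The visit-form-only path and the endpoint do not overlap: an event properly on that path is not device-related and cannot count. The route to the endpoint is the second row, and there the event is reported in detail. What can go wrong is its seriousness code.

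**Step 3. How close the endpoint is to its limit.**

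- Denominator: the safety population is all treated eyes (SAP Section 2.1), with a planned minimum of 334 (Protocol Section 4). The 300 evaluable eyes at stability are not the denominator of a cumulative endpoint in all treated eyes.
- 3/334 = 0.90%, which is below 1%: met.
- 4/334 = 1.20%: not met.

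A single eye coded non-serious changes the result only when the correct count is exactly 4. More generally, reversal needs enough miscoded eyes to bring a count of 4 or more down to 3.

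**Step 4. Illustration under assumed rates.** Let p be the true proportion of eyes with a serious, device-related event and m the share of those eyes coded non-serious. Treating eyes as independent, the chance of meeting the criterion is P(X ≤ 3) with X ~ Binomial(334, p(1 − m)).

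| p (assumed) | m = 0 | m = 25% | m = 50% |
|---|---|---|---|
| 1% | 57.1% | 75.7% | 91.2% |
| 2% | 9.8% | 26.2% | 57.1% |

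Neither p nor m comes from the documents. Eyes are treated in pairs (about 167 subjects), so independence is a simplification. The table shows how sensitive the criterion is to miscoding from any cause; it does not estimate what the Appendix L wording would do.

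**The case against.** The strongest reply is that Appendix L governs notification, not classification. Serious is formally defined once, in Section 11.1, and nothing says endpoint coding follows Appendix L. The heading of the Appendix L path itself uses the defined term. Section 11.3 states the 48-hour rule without narrowing, and its separate rule for unanticipated device effects is not narrowed either. For a device-related event to be miscounted, a site must prefer a parenthesis to the definition and the medical monitor, who reviews every such report and discusses it with the investigator as necessary, must leave the code uncorrected. Ongoing sponsor review of adverse event listings (Section 15.1) and verification of case report forms against source (Section 15.2) are further checks.

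Most of this stands, and it limits the endpoint part of the point. A reader might infer that serious events outside the Appendix L wording go onto the routine visit form and disappear from the primary safety endpoint. The documents do not support that: the routine form is for events that are not device-related, and a device-related event keeps its detailed form, monitor review and SAP listing. Nor does one criterion of six mean that most serious events are affected; that counts criteria, not events.

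Two things survive. The contradiction sits in the instruction sites are told to use, and other sections being right does not remove it. And although Section 15.3 has the monitor review and assess reports, neither document describes a check of seriousness against Section 11.1 before the endpoint is counted.

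**Conclusion.** The point holds as a modest internal inconsistency in safety reporting. Appendix L conflicts with Sections 11.1 and 11.3. Its direct consequence, for a site that follows it literally, is possible loss of the 48-hour notice for an event serious on another criterion. If such an event is also judged unrelated to the device, it may not reach the medical monitor.

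The effect on the primary safety endpoint is secondary and conditional. It requires a device-related event that meets only an omitted criterion, a site that codes it by the Appendix L wording, and no correction on review. Its size cannot be estimated, because the documents give no misclassification rate. It deserves attention because, at the planned minimum of 334 treated eyes, the boundary lies between 3 and 4 eyes.

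**What to change.** 1. **Protocol, Appendix L.** Reconcile the serious-event instruction with Sections 11.1 and 11.3 by replacing the parenthesis with a reference to the Section 11.1 definition, so that an event meeting any one of its criteria takes the 48-hour path.
2. **SAP, Section 5.2.** Add a sentence stating that seriousness for this endpoint follows Protocol Section 11.1, and that the seriousness code of every device-related event is checked against that definition before eyes are counted. These events are already in the SAP Section 6.13 listing and already go to the medical monitor, so only the explicit check is new.
3. **Sites.** Send a short memo pointing to the corrected instruction.

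The cost is a one-line protocol correction, one SAP sentence and the memo. Sample size, visits and procedures do not change.

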## NON-SERIOUS, DEVICE-RELATED EVENTS:

For events that are not considered serious but are believed related to the study device (ADEs):

- 1. Complete a Detailed Adverse Event Form
- 2. Ensure the data are submitted to AMO electronically within a timely manner.

17NOV2015/ 3.0 PR/STAR-115-MIPS

# APPENDIX M SCHIRMER I TEAR TEST (WITH ANESTHETIC)

Prepare the strips while they are still in the package by folding the rounded end at the indentation, approximately 5 mm from the tip. Open the plastic package and remove the strip for the right eye, holding the strip by the square-cornered end. Instill topical anesthetic solution into both eyes, wait for a few minutes for the drops to dissipate, and then insert the strips. Ask the patient to look up, gently retract the lower lid, and insert the strip into the inferior cul-de sac, placing the fold at the lid margin. Position the strip so that it is at the lateral third of the eyelid with the longer end hanging downward over the lower eyelid. As the strip is inserted, avoid touching any part of the eye. After inserting the remaining strip into left eye, the patient may gently close the eyes. Alternatively the patient may blink as desired but should avoid forceful lid closure. Dim the lights in the room to enhance patient comfort.

Leave the strips in place for 5 minutes or until the strips are completely wet, whichever occurs first. Ask the patient to look up, remove the strips from the inferior cul-de-sac, and measure the length of each strip that has been wetted by the tears, beginning the measurement at the notch. A measuring guide is found on the Schirmer strip package. A template of the strip next to the guide allows for accurate measurement of the amount of strip wetting. Alternatively, a millimeter rule may be used to measure the length of the strip wetted by the tears.

# Interpretation

A normal eye will wet between 10 and 30 mm of the strip and a severe dry eye will be wet less or equal to  $\leq 5$  mm in 5 minutes when the Schirmer I is performed.

#### Note:

Schirmer tear tests are performed before applanation tonometry or any other procedure that may irritate the cornea. If the topical ophthalmic anesthetic is not allowed to dissipate before inserting the strips, the amount of tears in the eye may be overestimated.

17NOV2015/ 3.0 55 PR/STAR-115-MIPS

# APPENDIX N INSTRUCTIONS FOR MONOCULAR CONTRAST SENSITIVITY TESTING USING THE VECTOR VISION SYSTEM

Monocular contrast sensitivity on the subject's first eye with the best distance correction in place (with refraction adjustment of +0.12 D added to the ETDRS refraction) will be measured using the Vector Vision self-illuminated light box and the Vector Vision Contrast Sensitivity charts, which contain a series of sine-wave gratings. The CSV-1000E chart tests four different spatial frequencies: A = 3 cycles/degree (cpd), B = 6 cpd, C = 12 cpd, and D = 18 cpd; whereas the CSV-1000-1.5CPD chart tests only one spatial frequency: E = 1.5 cpd. **The test distance is 8 feet (2.5 meters).** 

Contrast sensitivity will be tested under mesopic conditions with and without glare (1.5, 3, 6 and 12 cycles per degree) and photopic conditions without glare (3, 6, 12 and 18 cycles per degree).

A trial reading with the subject should be done prior to recording the testing data to ensure subject understanding of the test procedure.

Monocular contrast sensitivity testing will be measured with the subject's best distance correction (with a refraction adjustment of +0.12 D added to the sphere of the ETDRS refraction) in front of the eye being tested with the other eye occluded.

To measure monocular contrast sensitivity using the CSV-1000E chart, subjects are to identify which circle in each vertically-aligned circle set (1-8) contains the sine-wave pattern. The reference pattern for each spatial frequency is provided under the spatial frequency designation (A, B, etc.) on the chart. A similar pattern appears in either the top or bottom of each paired circle set, getting fainter and harder to see with each subsequent circle set. Subjects should be instructed to identify whether the top circle, bottom circle, or neither circle in each circle set contains the pattern. The subject should be prompted until no difference can be determined between the two circles in each set. Any incorrect response(s) prior to no difference being detected should be retested. For example, if a subject detects no difference at number 7, but responded incorrectly at number 4, the subject should be retested starting at number 3. After retesting, the number corresponding to the last correct response in a paired circle set is the score for that spatial frequency. If the subject is unable to see the reference pattern under the letter, then the score for that spatial frequency is zero. If the subject is able to see the reference pattern under the letter, but cannot identify any pattern in circle sets 1-8, then the score for that spatial frequency is the spatial frequency designation (A, B, etc.).

Note that the circle sets on the Vector Vision CSV-1000-1.5CPD chart are oriented sideby-side instead of being vertically aligned, so subjects should be instructed to identify whether the right circle, left circle or neither circle contains the pattern for this chart.

17NOV2015/ 3.0 56 PR/STAR-115-MIPS

NOTE: Spatial frequency testing is to be performed twice under each lighting condition. Score sheets must be retained as source documentation.

Mesopic testing without glare should be performed first, followed by mesopic testing with glare and lastly photopic testing without glare.

MESOPIC TESTING: Ensure room lighting is set to the proper level; typically all room lights are off or dimly lit with the exam-room door closed. In addition, the subject must view the test through the neutral density filter lenses, which will reduce the amount of illumination in the room to approximately 2.5 cd/m². After a recommended 10-minute adaptation period, mesopic testing may be performed. First use the CSV-1000-1.5CPD chart to test the spatial frequency of 1.5 cycles per degree. Then use the CSV-1000E chart to test the spatial frequencies of 3, 6 and 12 cycles per degree. (Testing at 18 cpd is not required for mesopic testing). Repeat mesopic testing without glare, and then perform and repeat mesopic testing with glare.

PHOTOPIC TESTING: Following mesopic testing, photopic testing without glare is to be performed and repeated. Room lighting should be set as low as possible with the majority of illumination from the light box. The illumination from the box is automatically calibrated at 85 cd/m2, but should be confirmed with the light meter (a range of 80-110 cd/m2 is acceptable). Continue to use only the CSV-1000E chart test face to test the spatial frequencies of 3, 6, 12 and 18 cycles per degree.

17NOV2015/ 3.0 57 PR/STAR-115-MIPS

1 INTRODUCTION

This document summarizes the statistical methods to be implemented during the analysis of data for the wavefront-guided PRK correction of myopic refractive errors with the iDesign Advanced WaveScan Studio System and STAR S4 IR Excimer Laser System (STAR-115-MIPS) study. This study will be a 12-month, prospective, multi-center, bilateral, open-label, non-randomized clinical trial. The key time point for reporting and submitting the PMA supplement will be at the time of refractive stability. At least 300 evaluable eyes at the point of refractive stability are intended for analyses. The primary effectiveness endpoints for this study are, monocular distance uncorrected visual acuity (UCVA), manifest refraction spherical equivalent (MRSE) predictability and refractive stability. The primary safety endpoints are the maintenance of best distance corrected visual acuity (BSCVA), rates of induced manifest refractive astigmatism and rates of serious device-related adverse events.

Other endpoints include monocular contrast sensitivity (substudy of 65 eyes), binocular UCVA, manifest cylinder, iDesign aberrometry, keratometry, intraocular pressure, anterior segment evaluation Schirmer I Tear Test (with anesthetic), ocular visual symptoms (non-directed and directed from the PRSVQ), and directed patient reported outcomes PROs: NEI-RQL-42, OSDI, and exploratory satisfaction questionnaires.

Table listings are included in Appendix I.

2 ANALYSIS POPULATIONS

2.1 ANALYSIS POPULATIONS/HANDLING OF MISSING DATA

The safety population will be the primary analysis population for all endpoints and includes all eyes that receive study treatment. However, if there are greater than 5% of eyes with missing study exams at the stability time point, an intent-to-treat (ITT) population will be used as the primary analysis population for the primary effectiveness endpoints. In this case, missing data will be imputed. For continuous variables, the planned method to use is the MCMC full-data imputation as described in Little & Rubin¹. For data with a binary response and a monotone missing pattern, the planned method is to use the monotone logistic regression multiple imputation method. Data imputation and analysis will be performed using the MI and MIANALYZE procedures² in SAS[®] (Version 9.2).

¹ Little, R. and Rubin, D. Statistical Analysis with Missing Data, John Wiley & Sons, Inc. New York, Second Edition, (2002)

² SAS Institute. The MI and MIANALYZE Procedures. SAS/STAT 9.2 User Guide. and SAS/STAT User Guide for the MI Procedure: Imputation Methods. Cary, N.C.

In addition to the above imputation methods, sensitivity analyses using different imputation approaches will also be performed for primary effectiveness endpoints for the ITT population. A worst-case scenario with the worst score assigned to the missing data will be performed. A tipping point analysis will also be performed.

2.2 VISIT SCHEDULE

All eyes will be examined preoperatively and at 1 day, 1 week, 1 month, 3 months, 6 months, 9 months and 12 months. The exact number of days for each interval is described in the protocol. The number of eyes with missing visits or data outside of the visit intervals will be reported.

2.3 DATA CONVENTIONS

Descriptive statistics will typically include sample size (N), mean, standard deviation (SD), median, minimum (Min.), and maximum (Max.) as appropriate for continuous variables. For categorical data, the frequency and proportion will be computed.

For continuous variables, statistical tests assuming normality will generally be used. However, the data will be reviewed to evaluate whether the normality assumption is appropriate. If it is found not to be appropriate, either an appropriate transformation of the data (i.e., logarithmic) may be used or the corresponding non-parametric tests may be used. Deviations from the proposed statistical guidelines will be substantiated by sound statistical rationale.

Unless otherwise indicated, alpha will be set to 0.05 for two-sided statistical testing.

For visual acuity data, ETDRS letter scores will be converted to LogMAR values prior to analysis. In addition, if the test distance used is not the standard test distance for the chart, then visual acuity data will be adjusted for the actual test distance used. Appendix II provides formulas for LogMAR conversion and distance adjustment.

For refractive data, all values will be converted to minus cylinder format and sphere will be adjusted for optical infinity. Formulas used for refractive data conversions are included in Appendix III.

